6. INVESTIGATORS AND STUDY ADMINISTRATION STRUCTURE

Information regarding the investigators, sites, laboratories, and other service providers is available upon request to the IRB/ECs and regulatory agencies.

7. INTRODUCTION

7.1. Indication

Liposome bupivacaine was developed to extend pain relief with a single dose administration without the use of indwelling catheters and to decrease the requirement for supplemental opioid medications. It is indicated for use as an analgesic injected into the surgical site for postsurgical pain relief. This study will explore the safety, efficacy, and pharmacokinetic (PK) profile of liposome bupivacaine when administered via a femoral nerve block.

Effective postsurgical pain control is a critical element in subject recovery following surgery, as the majority of subjects may experience significant pain, particularly in the first few days. Improved postsurgical pain management contributes to better healing, faster subject mobilization, shortened hospital stays, and reduced healthcare costs ([American Society of Anesthesiologists Task Force on Pain Management 1995](#)).

7.2. EXPAREL (bupivacaine liposome injectable suspension)

Bupivacaine is one of the longer-acting local anesthetics, but even so it has a limited duration of action after local administration, usually reported as less than 8 hours. EXPAREL[®] (Pacira Pharmaceuticals, Inc., San Diego, California) is a bupivacaine liposome injectable suspension. It consists of microscopic spherical, multivesicular liposomes (DepoFoam[®] drug delivery system), organized in a honeycomb-like structure comprising numerous non-concentric internal aqueous chambers containing a bupivacaine base at a concentration of 13.3 mg/mL. Each chamber is separated from adjacent chambers by lipid membranes. The lipids (phospholipids, cholesterol, and triglycerides) are naturally occurring or close analogs of endogenous lipids. Bupivacaine is slowly released from the DepoFoam particles by a complex mechanism involving reorganization of the barrier lipid membranes and subsequent diffusion of the drug over an extended period of time. A small amount of extra-liposomal bupivacaine (i.e., not bound within the DepoFoam particles) enables liposome bupivacaine to have a similar onset of action to standard bupivacaine.

EXPAREL (liposome bupivacaine) was approved by the US FDA in 2011 for administration into the surgical site to produce postsurgical analgesia. The active ingredient (bupivacaine) and inactive ingredient (DepoFoam) of EXPAREL are each contained, though separately, in FDA-approved products:

- Bupivacaine HCl solution, a well-characterized anesthetic/analgesic, with more than 35 years of use in the US.
- DepoFoam, a liposomal extended-release formulation contained in the marketed products DepoCyt[®] (1999) and DepoDur[®] (2004). The form of DepoFoam used in each of the three products – DepoCyt, DepoDur, and liposome bupivacaine – has a slightly different mixture of lipid components. However, unlike the other two products, EXPAREL employs a novel lipid excipient (dierucoylphosphatidylcholine [DEPC]) in its formulation.

7.3. Summary of Human Experience with Liposome Bupivacaine

Pacira has completed 21 clinical studies and 1 observational follow-up study to investigate liposome bupivacaine. Across these studies, over 1300 human subjects received liposome bupivacaine at doses ranging from 9 mg to 665 mg administered by various routes: local infiltration into the surgical wound, subcutaneous, perineural, and epidural. The product generally has been well tolerated and in active comparator studies reported adverse events (AEs) occurred at a similar rate as the corresponding bupivacaine HCl controls.

Two nerve block studies have been completed. SKY0402-002 was a Phase 1 dose escalation study conducted to evaluate the safety, pharmacodynamics, and pharmacokinetics of liposome bupivacaine. A total of 37 healthy subjects were administered liposome bupivacaine perineurally for unilateral ankle block in healthy male volunteers (24 subjects received liposome bupivacaine and 12 subjects received bupivacaine HCl). The incidence and types of adverse events experienced were similar across treatment groups. All AEs were mild or moderate in severity; those related to liposome bupivacaine were mild in severity. There were no serious adverse events (SAEs), deaths, or discontinuations due to adverse events.

SKY0402-C-203 was a Phase 2 nerve block study was performed in which three doses of liposome bupivacaine (155, 199, and 310 mg) were compared to bupivacaine HCl (125 mg) in a bunionectomy. A total of 38 patients received liposome bupivacaine. Liposome bupivacaine was well tolerated and several doses demonstrated statistically significant separation from bupivacaine HCl using multiple efficacy measures at multiple time points throughout the 72 hours; a PK curve also was defined.

In doses up to 665 mg, no adverse safety signal attributed to either the central nervous system or cardiovascular system was reported with liposome bupivacaine. Adverse events that are occasionally reported with high doses of standard bupivacaine solution have not been observed. In two rigorous QTc studies, liposome bupivacaine did not cause significant QTc prolongation even at the highest dose evaluated.

The robust nature of the efficacy results in both pivotal studies (SKY0402-C-316 and SKY0402-C-317) was demonstrated across subgroups of patients with various prognostic features and across demographic subgroups.

Following the NDA submission of EXPAREL (liposome bupivacaine), numerous clinical studies were initiated in which liposome bupivacaine was administered via various routes of administration (including infiltration into the transversus abdominis plane [TAP] and intraoperative wound infiltration or instillation); final results are not available at this time.

Please refer to the [Investigator's Brochure](#) for additional information regarding the completed studies. Please see the [EXPAREL Full US Prescribing Information](#) for safety information regarding the use of EXPAREL (liposome bupivacaine) in the setting of wound infiltration.

8. OBJECTIVES

8.1. Primary Objectives

Part 1: The primary objectives of Part 1 are to (1) evaluate three dose levels of liposome bupivacaine versus placebo with respect to the magnitude and duration of the analgesic effect achieved following single dose injection femoral nerve block with liposome bupivacaine, and (2) select a single therapeutic dose of liposome bupivacaine from the three dose levels to be tested in Part 2.

Part 2: The primary objective of Part 2 is to compare the magnitude and duration of the analgesic effect of single injection femoral nerve block of a single dose level of liposome bupivacaine (selected from Part 1) with placebo (preservative-free normal saline for injection).

8.2. Secondary Objectives

The secondary objectives are to evaluate additional efficacy parameters, characterize the PK profile of liposome bupivacaine when administered as a femoral nerve block, and further assess the safety profile of liposome bupivacaine.

9. STUDY DESIGN AND PLAN

9.1. Study Design

This is a Phase 2/3, multicenter, randomized, double-blind, parallel-group, placebo-controlled, dose-ranging study in subjects undergoing primary unilateral total knee arthroplasty (TKA) under general or spinal anesthesia. Note: Bupivacaine cannot be used as the spinal anesthetic.

On Day 1, eligible subjects will be randomized to receive a single dose of study drug administered within 2 hours prior to the surgical procedure as a femoral nerve block. Study drug administration will be performed in a blinded manner (see [Section 11.5.1](#)). At the conclusion of the block, a femoral nerve catheter is to be left in place and hep-locked (see “[Postsurgical Rescue Medication](#)” below). Additionally, a patient-controlled analgesia (PCA) pump will be established prior to the completion of the surgery. *The PCA pump will not be loaded at this time.* The use of fentanyl will be permitted during surgery. However, intraoperative administration of morphine or any other analgesics (including intrathecal opioids), local anesthetics, or anti-inflammatory agents is prohibited, unless needed to treat an AE.

All subjects will be required to remain in the study site for a minimum of 72 hours after the end of surgery for postsurgical assessments. The study staff will ensure adequate safety precautions are in place in order to prevent falls (e.g., use of support devices during ambulation, such as a knee immobilizer and walker/crutches) as needed.

Part 1

During Part 1 of the study, approximately 100 subjects (25 per treatment arm) will be randomized to receive a single dose injection femoral nerve block with either one of three doses of liposome bupivacaine (67, 133, or 266 mg) or placebo in 20 mL under ultrasound guidance. Preservative-free normal saline will be added to the 67 mg and 133 mg doses of study drug to achieve a volume of 20 mL.

After all subjects have completed the 72-hour assessments in Part 1, an analysis will be conducted in order to select a single therapeutic dose from the three liposome bupivacaine dose levels tested. An unblinded dose selection committee will review at least the results from the following assessments conducted during Part 1: (1) the area under the curve (AUC) of the numeric rating scale (NRS) at rest (NRS-R) pain intensity scores through 72 hours; (2) total postsurgical opioid consumption; (3) the time to first opioid rescue; and (4) safety data. Based on a clinical evaluation of the results the committee will determine the apparent efficacy and safety of each of the three liposome bupivacaine dose levels tested and will recommend a dose level for Part 2 of the study. Statistical significance will not be required in order to recommend a dose level for Part 2. The unblinded dose selection committee also will recommend whether the sample size for Part 2 should be increased.

Part 2

In Part 2 of the study, approximately 180 subjects (randomized 1:1, resulting in approximately 90 liposome bupivacaine subjects and 90 placebo subjects) will receive a single dose injection femoral nerve block with the selected dose of liposome bupivacaine (i.e., 67, 133, or 266 mg) or placebo in 20 mL under ultrasound guidance.

Postsurgical Rescue Medication

Subjects should only receive rescue medication upon request for pain control, as needed.

First Rescue Medication (IV Hydromorphone)

The first rescue medication will be intravenous (IV) hydromorphone 0.5 mg, which will be administered once via bolus only. At this time, the PCA should be loaded with opioid (morphine or hydromorphone only).

Second Rescue Medication (PCA and/or PO Opioid)

The second rescue medication will be an on-demand PCA-administered opioid (morphine or hydromorphone). The PCA pump will be programmed to deliver either on-demand morphine or on-demand hydromorphone boluses at a dose and lockout interval in accordance with the site's standard practice. A continuous infusion (background or basal rate) of morphine or hydromorphone is not permitted. If the subject's pain is excessive or pain control is inadequate, then the bolus dose may be adjusted according to local hospital practices; however, **adding a basal rate is prohibited.**

Once a subject is able to tolerate oral (PO) medication, PO immediate-release oxycodone may be administered (but not more than 10 mg every 4 hours).

Third Rescue Medication (Conventional Bupivacaine HCl)

If a subject's pain is inadequately controlled by opioids, a third rescue, a femoral nerve block, consisting of conventional bupivacaine HCl at a concentration of 0.125% (1.25 mg/mL) at a rate of 8 mL per hour for up to 12 hours may be administered via the previously placed femoral nerve catheter.

Subjects who do not receive adequate pain control with this regimen are to be withdrawn from the study and followed for AEs only. No other analgesic agents, including non-steroidal anti-inflammatory agents (NSAIDs), are allowed during the 72-hour observation period.

Postsurgical Assessments

Postsurgical assessments will include pain intensity scores using the 0-10 point NRS-R and NRS with activity (NRS-A) (where the prescribed activity is active knee flexion up to 45 degrees) (see [Appendix 1](#)); use of supplemental opioid pain medication; neurological assessment (see [Appendix 2](#)); cardiac assessment [i.e., ECG recordings]; sensory function assessment [i.e., cold test]; motor function assessment [i.e., 20-meter walk test]; vital signs; overall benefit of analgesia score (OBAS) questionnaire (see [Appendix 3](#)); subject satisfaction with postsurgical pain control (see [Appendix 4](#)); physician satisfaction with return of sensory/motor function (see [Appendix 5](#)); and an opioid-related AE questionnaire during Part 1 only (see [Appendix 6](#)). Adverse events will be recorded through Day 30. If a cardiac or neurological event occurs during Part 1 or Part 2 of the study that the Investigator believes may be associated with high levels of systemic bupivacaine, an unscheduled PK blood sample should be collected at the time that the event is noted.

Safety and efficacy assessments will be conducted at pre-specified time points *after the end of surgery* (defined as the time of last suture/staple). A follow-up visit will be scheduled for all subjects on Day 30.

Pharmacokinetic Assessments (Part 1 only)

Blood samples for PK analysis will be obtained from subjects at specific sites during Part 1 of the study at baseline, 15 minutes, 30 minutes, and 1, 2, 4, 8, 12, 24, 36, 48, 60, and 72 hours *after the beginning of study drug administration*. Blood samples for PK analysis should be collected even if the subject is not yet in surgery or is still in surgery. Placebo samples will be collected to maintain the treatment double-blind but will not be analyzed. Samples from subjects receiving bupivacaine nerve block rescue will not be analyzed. (Note: At time points when the PK and NRS pain intensity assessments coincide, the NRS pain intensity assessments will be conducted before the blood draw.)

Unscheduled blood samples also may be collected during Part 1 or Part 2 of the study if a cardiac or neurological event occurs that the Investigator believes may be associated with high levels of systemic bupivacaine.

9.1.1. Duration of the Study and Subject Participation

Each subject's participation in this study could be up to 64 days (up to 30 days for the screening period and up to 34 days for post-dosing follow-up).

9.1.2. Study Stopping Rules

No formal stopping rules are planned for this study. If, however, Pacira, the Investigator, or officials from regulatory authorities discover conditions during the study that indicate that the study or study site should be terminated, this action may be taken after Pacira has consulted with appropriate regulatory authorities and notified the Investigator(s).

9.2. Discussion of Study Design

Liposome bupivacaine is approved for infiltration into a surgical wound. This multicenter, randomized, double-blind, parallel-group study is a comparison of the efficacy and safety of liposome bupivacaine to placebo when administered as a femoral nerve block in subjects undergoing unilateral TKA. The double blind study design is intended to avoid potential bias resulting from subject or Investigator knowledge of the assigned treatment.

Total knee arthroplasty is a frequently performed surgical procedure that causes postsurgical pain of considerable intensity and duration. Standard analgesia following TKA often includes IV and PO opioids postoperatively. Therefore, TKA was selected as an appropriate pain model for investigating a sustained-release formulation of bupivacaine, which has the potential to overcome the limitation reported in previous studies with regard to the duration of the analgesic effect obtained with commercially-available products.

During Part 1, subjects will receive a single dose femoral nerve block with one of three dose levels of liposome bupivacaine (67, 133, or 266 mg). An unblinded dose selection committee will review study data, determine the apparent efficacy and safety of each of the three liposome bupivacaine dose levels tested, and recommend a dose level to be tested during Part 2 of the study. In Part 2 of the study, subjects will receive a single dose injection femoral nerve block with the selected dose of liposome bupivacaine (i.e., 67, 133, or 266 mg) or placebo.

All subjects will receive an opioid (morphine, hydromorphone, and/or oxycodone) and conventional bupivacaine HCl, as needed, to control breakthrough postsurgical pain.

Neurological and cardiac assessments will be conducted to rule out bupivacaine toxicity related to high plasma exposure. Additionally, sensory and motor function assessments will be conducted in order to test for restoration of nerve function.

10. STUDY POPULATION

10.1. Inclusion Criteria

Subjects eligible for study entry must meet all of the following criteria:

1. Male or female, ≥ 18 years of age.
2. Scheduled to undergo primary unilateral TKA under general or spinal anesthesia.
3. American Society of Anesthesiology (ASA) Physical Status 1, 2, or 3.
4. Able to demonstrate motor function by performing a 20-meter walk, unassisted with the optional use of a 4-legged walker, and sensory function by exhibiting sensitivity to cold.
5. Able to provide informed consent, adhere to the study visit schedule, and complete all study assessments.

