11.1.2. Study Drug Administration Considerations

Since there is a potential risk of severe adverse effects associated with the administration of bupivacaine, the study site must be equipped to manage subjects with any evidence of cardiac toxicity.

Administration of additional local anesthetics including bupivacaine or lidocaine is prohibited except where specified for spinal anesthesia or rescue. Bupivacaine cannot be used as the spinal anesthetic. Liposome bupivacaine may not be administered to a subject if it has been held in a syringe for more than 4 hours after preparation. In order to prevent the study drug from settling, gently inverting and re-inverting the syringe several times prior to administration is recommended.

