11.3. Method of Assigning Subjects to Treatment

11.3.1. Randomization Scheme

In Part 1 of the study, approximately 100 subjects (25 per treatment arm) will be randomized to receive a single dose injection femoral block with either one of three doses of liposome bupivacaine (67, 133, or 266 mg) or placebo.

In Part 2 of the study, approximately 180 subjects (randomized 1:1, resulting in approximately 90 liposome bupivacaine subjects and 90 placebo subjects) will be randomized to receive single dose injection femoral nerve block with the selected dose level (i.e., 67, 133, or 266 mg liposome bupivacaine) or placebo.

The randomization code will be generated by a centralized randomization system, which will also be used to communicate subject randomizations to study sites. All randomized subjects will have both a unique subject identifier and a unique random code identifier. No subject or random code identifiers are to be reused once assigned.

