13.5. Procedures After Surgery Through 72 Hours

Part 1 Only

- Question subject regarding the predefined treatment-emergent opioid-related AEs at 72 hours after surgery (see [Appendix 6](#)).
- Collect scheduled blood samples for PK analysis at specific sites only per [Section 12.3](#).

Parts 1 and 2

- Administer rescue medication for breakthrough pain per [Section 11](#).
- Load PCA pump with morphine or hydromorphone if IV hydromorphone 0.5 mg × 1 bolus is administered.
- Record date, time, and amount of all rescue medication administered (IV hydromorphone bolus, PCA opioid, oxycodone, and/or conventional bupivacaine HCl) through 72 hours after surgery.
- Record subject's assessment of pain intensity using the NRS-R followed by the NRS-A at the following time points: 2, 4, 8, 12, 24, 36, 48, 60, and 72 hours after surgery and at first request for rescue pain medication, if applicable (see [Appendix 1](#)).
- Perform neurological assessment at 15 minutes, 30 minutes, and 1, 2, 4, 8, 12, 18, 24, 30, 36, 42, 48, 60, and 72 hours after surgery per [Section 13.1.3](#) (see [Appendix 2](#)).
- Perform cardiac assessment (i.e., 12-lead digital ECG recordings) through 72 hours after study drug administration.
- Perform sensory function assessment (i.e., cold test) when the subject wakes up after surgery (general anesthesia subjects only), and at 2, 4, 12, 24, 36, 48, 60, and 72 hours after surgery, or until the subject's sensitivity to cold has returned to the baseline level in two consecutive evaluations per [Section 13.1.5](#).
- Perform motor function assessment (i.e., ability of subject to perform a 20-meter walk, unassisted with the optional use of a 4-legged walker) at 24 hours and 72 hours per [Section 13.1.6](#).
- Measure vital signs (heart rate and blood pressure) after subject has rested for at least 5 minutes in the supine position at 30 minutes, 1 hour, and 2 hours after surgery.
- Complete OBAS questionnaire (see [Appendix 3](#)) at 24, 48, and 72 hours after surgery.
- Obtain overall rating of subject satisfaction with postsurgical pain control using the Likert scale at 72 hours after surgery (see [Appendix 4](#)).
- Record AEs and any treatment(s) for the events.

- If a cardiac or neurological event occurs during Part 1 or Part 2 of the study that the Investigator believes may be associated with high levels of systemic bupivacaine, an unscheduled PK blood sample should be collected at the time that the event is noted.

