7.5. Measurements of Treatment Compliance

Study drug administration will be summarized by treatment group, separately for Part 1 and Part 2 for the safety analysis set. The variables to be included are duration of injection and volume of study drug administered. Surgery will be summarized by treatment group, separately for Part 1 and Part 2 for the efficacy analysis set. The variables to be included in the summary are length of surgery (end time minus start time, in minutes), type of anesthesia, and incision length.

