For the analysis of time to first opioid rescue, time to first opioid rescue will be computed in hours as the date/time of the first opioid rescue minus the date/time of the end of surgery. If a subject is not administered an opioid, the time to first administration will be censored at 72 hours after surgery or at the time of last follow-up, whichever is earliest. Time of last follow-up will be defined as the later of (1) the last pain assessment, (2) the start time of the last rescue or concomitant medication, or (3) the start time of the last AE.

Time to first opioid rescue will be analyzed by the Kaplan-Meier method. The n (%) of subjects administered an opioid as well as the n (%) of censored observations will be presented for each treatment group. In addition, Kaplan-Meier estimates in terms of the median and its 95% CI, and the 25th and 75th percentiles will be presented for each treatment. Log-rank tests will be used to compare each dose of liposome bupivacaine (Part 1) and the one dose of liposome bupivacaine (Part 2) to placebo.

For Part 2, the efficacy measures will be analyzed using a hierarchical fixed-sequence stepwise testing procedure. To protect the Type 1 error rate, the testing will be performed in a sequentially rejective fashion. First, the total postsurgical opioid consumption through 72 hours will be tested. If the test of opioid consumption is significant at the two-sided 0.05 level then, and only then, the time to first opioid rescue will be tested. Each test will be declared positive at the two-sided 0.05 significance level.

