The number and percentage of subjects who are in each of the above categories will be summarized by treatment group. A chi-square test will be used to compare liposome bupivacaine to placebo for each of the categories.

Overall Benefit of Analgesia Score Questionnaire

The OBAS is calculated as follows:

1. Add all of the scores of questions one to six.
2. To this number, add four.
3. Subtract the score of question seven from this number.

Summary statistics will be provided by treatment group at each time point. A Wilcoxon Rank Sum test will be used to compare liposome bupivacaine to placebo.

Subject Satisfaction with Postsurgical Pain Control

Subjects will rate their satisfaction with postsurgical pain control as Extremely dissatisfied, Dissatisfied, Neither satisfied nor dissatisfied, Satisfied, or Extremely satisfied at 72 hours and on Day 30. The categories will be summarized by treatment group at each time point. A Wilcoxon Rank Sum test will be used to compare liposome bupivacaine to placebo.

Time to Sensitivity to Cold

Once a subject reports sensitivity to cold on two consecutive evaluations the subject will no longer be tested. The time to sensitivity to cold will be defined as the time of the first of two consecutive evaluations when the subject reports sensitivity to cold. Time to sensitivity to cold will be calculated from the end of surgery. If a subject never reports sensitivity to cold or never reports sensitivity to cold on two consecutive evaluations then the time will be

censored at 72 hours after the end of surgery or at the time of the last follow-up, whichever is earliest. Time of last follow-up will be defined as the later of (1) the last pain assessment, (2) the start time of the last rescue or concomitant medication, or (3) the start time of the last AE.

Time to sensitivity to cold will be analyzed by the Kaplan-Meier method. The n (%) of subjects with sensitivity to cold as well as the n (%) of censored observations will be presented for each treatment group. In addition, Kaplan-Meier estimates in terms of the median and its 95% CI, and the 25th and 75th percentiles will be presented for each treatment group. For Part 2, a log-rank test will be used to compare liposome bupivacaine to placebo.

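### The Part 2 log-rank test of time to first opioid rescue is not stratified by anesthesia type; it loses power if that type is prognostic, which the documents do not establish

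*Protocol*

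**What the plan says.** Eligibility (Protocol 10.1, criterion 2) covers subjects "Scheduled to undergo primary unilateral TKA under general or spinal anesthesia". The one limit on the spinal agent is in Protocol 11.1.2: "Bupivacaine cannot be used as the spinal anesthetic".

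Protocol 11.3.1 says "The randomization code will be generated by a centralized randomization system" and plans "approximately 180 subjects (randomized 1:1, resulting in approximately 90 liposome bupivacaine subjects and 90 placebo subjects" for Part 2. Neither 11.3.1 nor 11.3.2 names a stratification factor.

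Time to first opioid rescue runs from the end of surgery and is censored at 72 hours or last follow-up. SAP 7.6.2.2 states: "Log-rank tests will be used to compare each dose of liposome bupivacaine (Part 1) and the one dose of liposome bupivacaine (Part 2) to placebo". Protocol 15.6.3.2 also specifies a log-rank test without strata. Under SAP 7.1.4 this endpoint is tested only if the primary endpoint and then 72-hour opioid consumption are both significant.

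Anesthesia type appears in the SAP as a descriptive surgery variable (7.5: "type of anesthesia, and incision length"). Tables 14.2.1.2-1 and 14.2.1.2-2 split it into General, Spinal and Other. SAP 7.1.5 keeps site out of every model.

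For the tertiary time to cold sensitivity, SAP 7.6.2.3 says "For Part 2, a log-rank test will be used to compare liposome bupivacaine to placebo". Protocol 13.5 schedules one cold test "when the subject wakes up after surgery (general anesthesia subjects only"); the first scheduled postsurgical test for the others is at 2 hours.

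**The concern.** A subject whose spinal has not fully worn off at the end of surgery might first ask for an opioid later than a general-anesthesia subject, whatever study drug was given. If so, each arm mixes early and late requesters. A log-rank test that ignores this compares arms within risk sets of unlike subjects; the apparent treatment effect shrinks toward the null and power falls. Stratifying compares like with like.

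At stake is the last formally tested claim of Part 2. Neither document gives a power, hazard ratio or event count for this endpoint, so no stated margin covers a loss.

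**Working it through.** **1. The plan's own figure.** Protocol 15.3 and SAP 8 give a difference of 61, SD 104, 90 per arm and two-sided 0.05. Power = Φ(61 / (104 × √(2/90)) − 1.96) = Φ(3.935 − 1.96) = 97.6%; the noncentral t gives 97.5%. The stated >97% reproduces. It concerns the primary AUC only.

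**2. Benchmark for the log-rank test.** If nearly all 180 subjects have an event, Schoenfeld power = Φ(|ln HR| × √(180/4) − 1.96). The hazard ratios are assumptions.
- HR 0.60: Φ(3.427 − 1.96) = 92.9%
- HR 0.65: Φ(2.890 − 1.96) = 82.4%
- HR 0.70: Φ(2.393 − 1.96) = 66.7%

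**3. Simulation of the planned and the stratified test.** From the documents: 180 subjects, 1:1, censoring at 72 h, two-sided 0.05. Assumed: exponential times, median 1 h in general-anesthesia placebo subjects, treatment HR 0.65, 25% or 50% spinal. Spinal either multiplies the rescue hazard or adds a delay (uniform from 0.5 to 1.5 times its mean). There were 4,000 runs per scenario with unstratified randomization, so chance imbalance is included. The statistic is |U|/√V, with U = Σ(g − p) and V = Σp(1 − p) over events, where g is the treatment indicator and p the treated fraction at risk. The stratified test sums U and V over anesthesia types.

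| Assumed spinal effect | Unstratified, 25% / 50% spinal | Stratified, 25% / 50% spinal | Loss (points) |
|---|---|---|---|
| None | 81.1 / 80.2 | 80.2 / 78.9 | −0.9 / −1.3 |
| Delay, mean 1 h | 78.8 / 77.0 | 79.6 / 79.5 | 0.8 / 2.5 |
| Hazard × 0.50 | 75.8 / 73.4 | 81.5 / 80.5 | 5.7 / 7.1 |
| Delay, mean 2 h | 72.0 / 70.5 | 79.5 / 79.1 | 7.5 / 8.6 |
| Hazard × 0.33 | 65.0 / 66.1 | 79.6 / 80.8 | 14.6 / 14.7 |
| Delay, mean 3 h | 60.0 / 59.2 | 77.5 / 76.5 | 17.5 / 17.3 |
| Hazard × 0.25 | 58.8 / 58.9 | 80.6 / 79.9 | 21.8 / 21.0 |

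At HR 0.60 the same scenarios give 74–92% unstratified and 90–92% stratified.

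**4. Where the loss disappears** (HR 0.65, 40% spinal unless stated; unstratified vs stratified).
- 1 h delay: 78% vs 80% with a control median of 1 h, 80% vs 80% at 2 h, 82% vs 81% at 4 h.
- 2 h delay: 68% vs 77%, 78% vs 80% and 81% vs 81% at the same medians.
- Spinal times longer by a constant ratio, control median 1 h: 81% vs 81% at ratio 1.25 and 78% vs 80% at ratio 1.5.
- Ratio 2 with 90% spinal: 79% vs 80%.

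**5. Type I error.** Under no treatment effect and unstratified randomization, the planned test rejected in 4.7–6.1% of runs over 14 scenarios (average 5.3%). The stratified test rejected in 4.6–5.9% (average 5.2%). Both are close to nominal.

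**6. Stratifying the randomization only.** At HR 0.65 the unstratified test moved little: 58.8% to 58.8%, 66.1% to 66.7%, and at most 60.0% to 64.7% (2,000 runs). Under no treatment effect that combination rejected in only 1.1–5.2% of runs, so it can be conservative. The power comes from stratifying the test.

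**The case against.** The strongest reply is that the premise is missing. A reader might infer that general and spinal subjects start the clock in very different states and that the power loss is a fact. The documents do not support that: they report no spinal share, block duration or rescue time by type, and they bar bupivacaine as the spinal agent. A reader might also take the wake-up cold test as the protocol's admission of residual spinal block. The plainer reading is that only general-anesthesia subjects have a wake-up time. Both points stand, so the concern is conditional.

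The mechanism is also temporary. A delay that is short relative to the usual time to first request costs little or nothing (step 4). This stands too.

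Nor is criterion 2 the flaw. Enrolling both types is legitimate, and the text to change is SAP 7.6.2.2. The criterion also does not prove that the choice between the two is fixed before randomization, and no planned-type field is shown. SAP 7.1.3 describes PCA data already collected, so capture before assignment may be too late for many subjects.

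Finally, the planned test is valid and is reached only after two earlier successes. That limits the priority of the point. It does not remove it, because the alternative test costs almost nothing and can be prespecified credibly only while the blind holds.

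**Conclusion.** The concern holds in conditional form. The Part 2 test of time to first opioid rescue leaves out a recorded variable that could be prognostic, and it loses power if that variable is.

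With HR 0.65, 25–50% spinal and a 1 h control median, all assumed, the loss runs from none to about 22 points. It reaches 6–9 points if spinal halves the hazard or delays rescue by 2 h. It is about 15–22 points if spinal cuts the hazard to one third or one quarter, or delays rescue by 3 h. It is close to nil if spinal has no effect, if the delay is short relative to the control median, or if nearly all subjects have one type.

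This is a question of efficiency. The results show no inflation of type I error and leave the primary power statement untouched. For time to cold sensitivity, the assessment schedule itself differs by anesthesia type, but no gain has been quantified: that endpoint is observed only at scheduled visits, so the simulation above does not describe it.

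**What to change.** Before the blind is broken, amend SAP 7.6.2.2 for Part 2:

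1. Make the test of time to first opioid rescue a log-rank test stratified by anesthesia type (general, spinal).
2. State in advance how subjects recorded as Other are assigned to a stratum.
3. Keep the overall Kaplan-Meier summaries, and report the unstratified log-rank test as a sensitivity analysis.
4. Use the planned type recorded before assignment wherever it can still be captured. For subjects already randomized, use the recorded type and state that it is set around or after dosing. This matters because Protocol 11.1.1 has the anesthesiologist give the study drug and 11.5.1 says active and placebo look different.
5. Record the change from the unstratified test in Protocol 15.6.3.2.

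The same stratification may be applied to time to cold sensitivity in SAP 7.6.2.3. Stratifying the randomization is optional and adds little power; if it is done, the test should be stratified to match.

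The cost is a few sentences in the SAP and, where still feasible, one field at randomization. It needs no added subjects or assessments. The statistical price is about 1 point of power if anesthesia type is not prognostic, and a negligible loss of information if one stratum is very small.
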